10. MEASUREMENT OF EFFECT

Response criteria will follow the International Harmonization Project for Lymphoma criteria²⁶ (see Appendix C) using CT scans of the chest, abdomen, and pelvis.

11. ADVERSE EVENT REPORTING REQUIREMENTS

11.1 Definitions

11.1.1 Adverse Event (AE)

An adverse event (AE) is any undesirable sign, symptom or medical condition or experience that develops or worsens in severity after starting the first dose of study treatment or any procedure specified in the protocol, even if the event is not considered to be related to the study.

Abnormal laboratory values or diagnostic test results constitute adverse events only if they induce clinical signs or symptoms or require treatment or further diagnostic tests.

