6.1 Anticipated Toxicities from Imprime PGG

A list of the adverse events and potential risks associated with Imprime PGG appear below and will determine whether dose delays and modifications will be made or whether the event requires expedited reporting **in addition** to routine reporting.

- Less likely toxicities (5-20%)
 - Increase in Aspartate Aminotransferase (AST) and Alkaline phosphate (ALK) levels in the blood
 - Skin rash or dry skin
 - Diarrhea
 - Electrolyte disturbances: decrease in potassium, magnesium, and/or phosphate levels in the blood
 - Hair loss
 - Anemia
 - Decreased appetite
 - Increase in amylase levels in the blood
 - Headache
 - Allergic reaction
 - Hypertension
 - Dyspnea
 - Conjunctivitis
 - Increased or decreased number of white blood cells
 - Mouth sores
 - Nausea or vomiting
 - Swelling around finger nails
 - Arthralgia
 - Fever

CONFIDENTIAL

This document is confidential. Do not disclose or use except as authorized.

- Rare but serious toxicities (<5%)
 - Dehydration
 - Fluid around the lungs
 - Blood clot that travels to the lungs
 - Death (refer to Section 2.1.1.3)

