6.3.2 Hematologic toxicities

The only hematologic parameter that must be met on each treatment day is an ANC ≥ 1000 . Hematologic toxicities should be managed by standard use of transfusions and growth factors. In particular, white blood cell growth factor use (e.g., neupogen) is acceptable on this study. A dose delay of up to 1 week for recovery of neutropenia to an ANC ≥ 1000 is acceptable on this study.

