6.3.3 Non-hematologic toxicities

In the case of asymptomatic laboratory abnormalities (e.g., LFT abnormalities), no intervention is required. Symptomatic abnormalities should be managed using standard clinical guidelines.

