14. STATISTICAL CONSIDERATIONS

14.1 Study Design/Endpoints

This is an open-label, single-arm, phase II clinical trial of Imprime PGG in combination with rituximab in patients with relapsed/refractory indolent B cell non-Hodgkin lymphomas. The primary endpoint is efficacy as measured by overall response rate. Secondary endpoints will include response duration, progression free survival at 1 year, , and rate of grade III and IV adverse events or discontinuation due to toxicity. We will estimate the proportion of patients alive without progression at 12 months after study entry. All patients must be followed for a minimum 12 months and must have scans at 6 and 12 months. No patients will be censored for this assessment. The one-year rate of being alive without progression will be estimated as a binomial proportion, and an exact binomial 90% confidence interval will be provided.

Patients will be accrued in a single stage design, with a goal accrual of 25 patients. Assuming a 30% response rate with rituximab alone, if the true but unknown rate of CR or PR is 50% with the addition of Imprime PGG, the probability of observing 11 or more patients with a response is 0.79. Therefore a study with 25 patients, in which an observed response rate of 11/25 (44%) would be considered worthy of further consideration.

We propose correlative studies quantifying Imprime PGG-bound and activated neutrophils, comparing both to the number and activation of unbound neutrophils from the same patient. We can examine the association between response to therapy (CR/PR vs. SD/Progression as best response).

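### Grade 3-4 laboratory values that are asymptomatic, untreated and not further tested fall outside the adverse-event definition, so the secondary grade III/IV rate may be under-counted

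*Combined protocol and SAP*

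**What the plan says.** Section 11.1.1 sets the test for laboratory findings: "Abnormal laboratory values or diagnostic test results constitute adverse events only if they induce clinical signs or symptoms". The sentence then gives two alternatives: "or require treatment or further diagnostic tests". Any one of the three conditions is enough, and none refers to grade.

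Section 6.3.3, on non-hematologic toxicity, says: "In the case of asymptomatic laboratory abnormalities (e.g., LFT abnormalities), no intervention is required". It also sets no grade limit.

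Section 14.1 includes among the secondary endpoints the "rate of grade III and IV adverse events or discontinuation due to toxicity". It gives no separate rule for laboratory toxicity, so the endpoint inherits the definition in 11.1.1.

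Section 6.1 lists several laboratory findings as anticipated from Imprime PGG, in a band of 5-20%. They include "Increase in Aspartate Aminotransferase (AST) and Alkaline phosphate (ALK) levels in the blood", "Electrolyte disturbances: decrease in potassium, magnesium, and/or phosphate levels in the blood" and "Increase in amylase levels in the blood", as well as anemia and white-cell changes. Section 11.1.3.1 refers to this list as the expected adverse events.

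**The concern.** Whether a severe laboratory value enters the safety endpoint depends on how the clinician responds to it and not on its grade. A high-grade AST rise that is simply watched is not an adverse event; the same value followed by an extra test is. Two investigators could therefore classify identical results differently while both follow the protocol.

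The error can run in one direction only, because the rule removes events and never adds them. It also falls on findings that the protocol names for the study drug. Safety of the combination is a stated secondary objective (Section 1.3), and with 25 patients the reported rate moves noticeably with each patient.

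**Working it through.** **Plan's own figures.** The documents state no expected grade III/IV rate and no precision for it, so there is no safety figure to reproduce. The one design figure, in Section 14.1, does reproduce. The exact binomial probability of 11 or more responses in 25 at a true rate of 50% is 0.788, against the stated 0.79; at 30% it is 0.098. Nothing in this point touches that calculation.

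**Following a value through the text.** Take an AST value of CTCAE grade 3 or 4 in a patient without symptoms.

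1. Signs or symptoms (11.1.1): no.
2. Requires treatment (11.1.1): under 6.3.3, no intervention is required. If the clinician treats anyway, the value can qualify.
3. Requires further tests (11.1.1): 6.3.3 is silent on this. If the value is worked up, it qualifies; if it is only seen again at the next scheduled draw, the text does not clearly make it qualify.
4. If all three answers are no, the value is not an adverse event and does not reach the 14.1 rate.

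**Whether another section closes the gap.**

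- Section 11.2 records and grades adverse events, including those found by laboratory test, but only once they are adverse events.
- Section 11.4.2 adds grade 2 and 3 events to expedited reporting only if they are unexpected and related. The 6.1 findings are expected. Its grade 4 clause does not say whether a laboratory value that fails 11.1.1 is an event.
- Section 14.2 counts grade 4 non-hematologic toxicity without saying whether laboratory values are included.

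None of these overrides 11.1.1.

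**Size per patient.** With a denominator of 25 (Section 14.3), one missed patient is 1/25 = 4 percentage points. This applies only if the patient has no other grade 3-4 event and, if the endpoint is read as a composite, did not stop treatment for toxicity. For scale, 3/25 is 12% with an exact 90% interval of 3.4% to 28.2%, and 2/25 is 8% with 1.4% to 23.1%.

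**Illustration under assumptions.** Let q be the rate of patients with another grade 3-4 event, l the rate of laboratory-only grade 3-4 values among the rest, and s the share of those that 11.1.1 excludes. None of the three is in the documents.

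- Full rate = q + (1 - q) × l
- Reported rate = q + (1 - q) × l × (1 - s)
- Shortfall = (1 - q) × l × s

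With q = 10%:

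| l | s | Full rate | Reported rate | Shortfall (points) | Patients of 25 |
|---|---|---|---|---|---|
| any | 0 | equal | equal | 0 | 0 |
| 5% | 0.5 | 14.5% | 12.3% | 2.3 | 0.6 |
| 5% | 1 | 14.5% | 10.0% | 4.5 | 1.1 |
| 10% | 0.5 | 19.0% | 14.5% | 4.5 | 1.1 |
| 10% | 1 | 19.0% | 10.0% | 9.0 | 2.3 |
| 20% | 1 | 28.0% | 10.0% | 18.0 | 4.5 |

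For example, l = 10% and s = 1 gives 0.90 × 0.10 × 1 = 0.09, and 25 × 0.09 = 2.25 patients. With q = 20% and s = 1, the shortfalls at l = 5%, 10% and 20% are 4, 8 and 16 points. The table shows how the shortfall behaves; it is not an estimate.

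**The case against.** The strongest reply is that 11.1.1 is an explicit choice to count laboratory findings with clinical consequences, and that it leaves little out. Its three conditions are alternatives. Section 6.3.3 says that intervention is not required; it does not forbid treatment and does not mention tests. Section 6.3 defers to standard practice, toxicity is assessed at every visit, and 11.2 grades by CTCAE v4.0. The rate is also a descriptive secondary endpoint with no threshold.

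Much of this stands, and it rules out several stronger readings.

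- A reader might infer that asymptomatic grade 3-4 laboratory values are excluded as a class. They are not: treatment or further testing brings them in.
- A reader might extend the point to cytopenias. Section 6.3.3 covers non-hematologic findings only. Section 6.3.2 manages hematologic toxicity with transfusions and growth factors, and treated cases count. Neutropenia that is waited out is arguable: 6.3.2 allows "A dose delay of up to 1 week for recovery of neutropenia", but the delay ends only on a repeat count, which may itself be a further test.
- A reader might apply the 5-20% band in 6.1 to 25 patients and conclude that the rate is 4 to 20 points too low. The band carries no grade restriction and applies to each listed toxicity, so it is neither a grade 3-4 rate nor an upper bound on the combined rate. Zero is possible.
- A reader might conclude that the rate cannot be compared with other studies. That depends on how those studies counted laboratory values, which the documents do not say.

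What the reply does not remove is the residual class of values that are asymptomatic, untreated and not further tested. The case report forms might capture them, but they are not part of the documents.

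**Conclusion.** The concern holds in this limited form: by definition, some grade 3-4 non-hematologic laboratory values can fall outside the adverse-event count, and the secondary grade III/IV rate may be too low as a result. The findings most exposed are AST/ALK rises and electrolyte falls; an amylase rise is exposed where amylase is measured.

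The size cannot be derived from the documents. It is 4 points per affected patient with no other qualifying event, on an assumed denominator of 25, and the total may be zero. The 0 to 18 point range in the working rests wholly on assumed inputs. The documents support saying that the rate may be under-counted, not that it will be. Response rate, sample size and the 11-of-25 rule are unaffected.

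**What to change.** In Section 14.1, state that the worst CTCAE v4.0 grade after the first dose will be derived from the blood count and metabolic panel results already scheduled, and that grade 3-4 laboratory values count in the safety rate whether or not they met 11.1.1. Show patients whose only grade 3-4 finding is a laboratory value on a separate line, so that the rate under the present definition can still be read off. In keeping with 11.1.1, count values that are new or worse than at baseline.

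Section 9 names the blood count, complete metabolic panel and LDH. It does not name amylase, magnesium or phosphate, so these should be graded only where they were measured, and the report should say so.

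In Section 14.2, state whether the grade 4 non-hematologic toxicity count uses the same definition.

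The cost is a few sentences, some extra analysis and a safety rate that may look less favourable. No new blood draws are needed and patient management does not change.

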11.1.2 Serious adverse event (SAE)

A serious adverse event (SAE) is any adverse event, occurring at any dose and regardless of causality that:

- Results in death
- Is life-threatening. Life-threatening means that the person was at immediate risk of death from the reaction as it occurred, i.e., it does not include a reaction which hypothetically might have caused death had it occurred in a more severe form.

CONFIDENTIAL

This document is confidential. Do not disclose or use except as authorized.

- Requires or prolongs inpatient hospitalization (i.e., the event required at least a 24-hour hospitalization or prolonged a hospitalization beyond the expected length of stay). Hospitalization admissions and/or surgical operations scheduled to occur during the study period, but planned prior to study entry are not considered SAEs if the illness or disease existed before the person was enrolled in the trial, provided that it did not deteriorate in an unexpected manner during the trial (e.g., surgery performed earlier than planned).
- Results in persistent or significant disability/incapacity. Disability is defined as a substantial disruption of a person's ability to conduct normal life functions.
- Is a congenital anomaly or birth defect; or
- Is an important medical event when, based upon appropriate medical judgment, it may jeopardize the participant and require medical or surgical intervention to prevent one of the outcomes listed above. Examples of such medical events include allergic bronchospasm requiring intensive treatment in an emergency room or at home; blood dyscrasias or convulsions that do not result in inpatient hospitalization, or the development of drug dependency or drug abuse.

Events **not** considered to be serious adverse events are hospitalizations for:

- routine treatment or monitoring of the studied indication, not associated with any deterioration in condition, or for elective procedures
- elective or pre-planned treatment for a pre-existing condition that did not worsen
- emergency outpatient treatment for an event not fulfilling the serious criteria outlined above and not resulting in inpatient admission
- respite care

11.1.3 Expectedness

Adverse events can be 'Expected' or 'Unexpected.'

11.1.3.1 Expected adverse event

Expected adverse events are those that have been previously identified as resulting from administration of the agent. For the purposes of this study, an adverse event is considered expected

CONFIDENTIAL

This document is confidential. Do not disclose or use except as authorized.

when it appears in the current adverse event list, the Investigator's Brochure, the package insert or is included in the informed consent document as a potential risk.

Refer to Section 6.1 for a listing of expected adverse events associated with the study agent(s).

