health decline, nausea, pneumonia, pneumothorax, diarrhea, dyspnea, lung embolism, neutropenia, pleural effusion, and pulmonary embolism. Among these, the following occurred in more than 5% of patients: general health decline (6.8%), diarrhea (6.7%), neutropenia (6.7%), and pleural effusion (6.7%). Eighteen (18) deaths have been reported in studies with Imprime PGG, including one that occurred prior to a subject receiving any study-related medications. Of these, 15 deaths occurred in the NSCLC studies: 7 in LCA0821 (Imprime PGG with bevacizumab \pm chemotherapy) and 8 in LCA0822 (Imprime PGG with cetuximab \pm chemotherapy). In LCA0821, deaths were the outcome of general health deterioration (N=3, investigational arm), disease progression (N=1, investigational arm), intracranial hemorrhage (N=1, investigational arm), pneumonia (N=1, investigational arm), and pneumothorax (N=1, investigational arm). In LCA0822, deaths were the outcome of sepsis following severe neutropenia and acute renal failure (N=1, investigational arm), acute cardiovascular failure (N=1, investigational arm), disease progression (N=1, control arm), hemoptysis (N=2, investigational arm), pleural effusion (N=1, investigational arm), and pulmonary hemorrhage (N=1, investigational arm). To date, three deaths have occurred in study CRC1031 (Phase 3 mCRC). The deaths were the outcome of bilateral bowel perforation (N=1, investigational arm), cardiac arrest (N=1, investigational arm), and pneumonia (N=1, investigational arm).

In dose escalation studies (2mg/kg, 4mg/kg and 6mg/kg); no maximally tolerated dose has been achieved. Biothera has opted to proceed with the 4mg/kg dose based on tolerability and efficacy data showing that this dose is more efficacious than the 2mg/kg and 6mg/kg doses.

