11.1.3.2 Unexpected adverse event

For the purposes of this study, an adverse event is considered unexpected when it varies in nature, intensity or frequency from information provided in the current adverse event list, the Investigator's Brochure, the package insert or when it is not included in the informed consent document as a potential risk.

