- After protocol-specified procedures begin (e.g. placebo run-in, washout period, double-blind treatment) and until at least 28 days after the patient has stopped study treatment
- After the start of any period in which the study protocol interferes with the standard medical treatment given to a patient (e.g. treatment withdrawal during washout period, change in treatment to a fixed dose of concomitant medication) and until at least 28 days after the patient has stopped study treatment

Any SAEs experienced after this 28-day period should only be reported to Biothera if the investigator suspects a causal relationship to the study drug. Recurrent episodes, complications, or progression of the initial SAE must be reported as follow-up to the original episode within 24 hours of the investigator receiving the follow-up information.

An SAE occurring at a different time interval or otherwise considered completely unrelated to a previously reported one should be reported separately as a new event.

Information about all SAEs is collected and recorded on the Med Watch 3500A Form. The investigator must assess and record the relationship of each SAE to each specific study drug, complete the Med Watch Form in English, and fax the completed form within 24 hours to [name] at [contact].

All SAEs will have to be submitted to Apcer to be included in our safety database. SAEs need to be transmitted to APCER via email to [contact] or via fax to [contact]

CONFIDENTIAL

This document is confidential. Do not disclose or use except as authorized.

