11.6 Reporting to the Food and Drug Administration (FDA)

The DF/HCC Overall Principal Investigator, as holder of the IND, will be responsible for all communication with the FDA. The DF/HCC Overall Principal Investigator will report to the FDA, regardless of the site of occurrence, any adverse event that is serious, unexpected and reasonably related (i.e., possible, probable, definite) to the study treatment.

Unexpected fatal or life-threatening experiences associated with the use of the study treatment will be reported to FDA as soon as possible but in no event later than 7 calendar days after initial receipt of the information.

All other serious unexpected experiences associated with the use of the study treatment will be reported to FDA as soon as possible but in no event later than 15 calendar days after initial receipt of the information.

Events will be reported to the FDA by telephone ([name]) or by fax ([name]) using Form FDA 3500A (Mandatory Reporting Form for investigational agents). Forms are available at <http://www.fda.gov/medwatch/getforms.htm>.

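### Expected and unexpected adverse events are defined by overlapping rules not tied to the suspected drug, so a serious Imprime PGG event listed only for rituximab may miss its expedited FDA report

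*Combined protocol and SAP*

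**What the plan says.** Section 11.1.3.1 starts from a single product: "Expected adverse events are those that have been previously identified as resulting from administration of the agent". Its working rule is wider. An event is expected "when it appears in the current adverse event list, the Investigator's Brochure, the package insert or is included in the informed consent document". The section closes with a pointer, "Refer to Section 6.1 for a listing of expected adverse events associated with the study agent(s", but Section 6.1 covers Imprime PGG only. The rituximab list is in Section 6.2 and is not mentioned there.

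Section 11.1.3.2 makes an event unexpected if it differs in kind, severity or rate from what the adverse event list, brochure or insert says, "or when it is not included in the informed consent document as a potential risk".

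Section 11.6 limits expedited FDA reporting to "any adverse event that is serious, unexpected and reasonably related (i.e., possible, probable, definite) to the study treatment". Section 11.1.4 likewise attributes events to the study treatment as a whole. Causality is recorded by drug on the SAE form (Section 11.4.2: "The investigator must assess and record the relationship of each SAE to each specific study drug"), but the protocol does not ask for expectedness by drug.

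**The concern.** Expectedness decides whether a serious, related event goes to the FDA on the 7- or 15-day clock. If it is judged against a pool of sources for both drugs, a new harm of the investigational drug can be treated as already known because the marketed partner has it on its list.

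This trial is exposed to that problem. Imprime PGG is infused first, and rituximab may start 10 to 15 minutes later (Section 5). The two toxicity profiles overlap: allergic reactions and rash were among the commonest reasons for stopping in earlier Imprime PGG cancer studies (Section 2.1.3). With a single arm, no control group would show an excess of events that rituximab alone can cause. Recognizing new Imprime PGG toxicity therefore depends heavily on how individual events are classified.

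**Working it through.** No arithmetic applies. The check sets the definitions beside the toxicity lists and follows three kinds of event through them.

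**Inputs**
- Package insert: cited for rituximab (Sections 7.2.1 and 7.2.3). Section 7.1.5 describes Imprime PGG as investigational, and no insert is cited for it.
- Lists: tumor lysis syndrome and cardiogenic shock are in Section 6.2 and not in Section 6.1.
- Use of the lists: the introduction to Section 6.2 says the rituximab list helps decide which events need expedited reporting. It does not restrict this to events attributed to rituximab.
- Assumption for case A: the event is not in the Imprime PGG Investigator's Brochure, which is not among the documents.

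**Trace**

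| Case | 11.1.3.1, working rule | 11.1.3.1, opening sentence and pointer | 11.1.3.2 |
|---|---|---|---|
| A. Serious, suspected due to Imprime PGG, listed only for rituximab | Expected (in the insert or Section 6.2) | Not expected (not identified for that agent, not in Section 6.1) | Unexpected if judged to differ from the brochure or the Imprime PGG list, or if absent from the consent form |
| B. In the insert, absent from the consent form | Expected | Depends on the drug | Unexpected |
| C. Listed, but more severe than described | Expected (it appears) | Expected if listed for that agent | Unexpected |

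Cases B and C meet both definitions. In case A the answer depends on which sentence is applied, so two investigators could follow the text and reach opposite conclusions about the FDA report.

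**What depends on the classification**
- The 7- and 15-day FDA reports (Section 11.6).
- The added 24-hour report of related grade 2 and 3 events, which is limited to unexpected ones (Section 11.4.2).
- The list of unexpected events of grade 2 or higher that may go to the DSMC (Section 12.2).

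**What does not**
- SAE reports to the Overall Principal Investigator and to Biothera within the stated windows (Section 11.4.2).
- SAE reports to the IRB office, OHRS (Section 11.5).
- Non-serious events, which reach the Overall Principal Investigator on case report forms (Section 11.4.3).

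The main exposure is therefore the FDA report. The Overall Principal Investigator holds the IND and receives the SAE in any case, but then has to apply these definitions to decide whether to forward it.

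**The case against.** The strongest reply is that the text does not pool the two drugs outright. Section 11.1.3.1 opens with one agent and points to the Imprime PGG list, and Section 11.1.3.2 gives an independent route to unexpected. A reader might infer that an Imprime PGG event listed only for rituximab always counts as expected and always misses the FDA report. The documents do not support that; the result is indeterminate. This part of the reply stands, but it does not remove the problem, because nothing says which rule prevails.

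Other safeguards do not use expectedness. Three or more grade 4 non-hematologic toxicities, or any grade 5 toxicity, suspend the study (Section 14.2). A grade 4 event escapes the Section 11.4.2 report only if it is expected and also named in the protocol as exempt, and the documents show no such list. The DSMC reviews toxicity data generally. These safeguards stand, and they narrow the gap to the reports named above. In particular, a reader might infer that non-serious grade 2 and 3 events could go unreported to the Overall Principal Investigator. Section 11.4.3 rules that out; only the 24-hour route is lost.

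A reader might also infer that every event in Section 6.2 is affected. That is not supported. Section 6.1 already includes allergic reaction, dyspnea, rash and white-cell changes. Section 2.1.3 reports deaths involving acute renal failure, acute cardiovascular failure and cardiac arrest on Imprime PGG, so its brochure may cover some cardiac and renal events, possibly including cardiogenic shock.

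Finally, Section 6.1 puts "Fluid around the lungs" below 5%, while Section 2.1.3 gives 6.7% for pleural effusion among serious events. It is tempting to use this as evidence that the frequency test fails. Pleural effusion is not in the rituximab list, so it says nothing about pooling, and the 6.7% is an SAE rate without a stated denominator set against a general band. It is not relied on here.

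**Conclusion.** The point holds as a defect in the definitions with a specific consequence. The rules for expected and unexpected are not complements, neither is tied to the suspected drug, and the pointer to Section 6.1 does not match its reference to more than one agent. Following the text can lead to a missed expedited FDA report for a serious event suspected to be due to Imprime PGG and listed only for rituximab. The added 24-hour report of grade 2 and 3 events and the DSMC listing are exposed in the same way.

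No number can be put on it: the brochure, the insert and the consent form are not available, so the listing of any given event cannot be checked. The tumor lysis syndrome and cardiogenic shock examples rest on the assumption that the brochure does not list them. Sample size, power and the efficacy analysis are unaffected.

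**What to change.** In Section 11.1.3:

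1. Judge expectedness separately for each suspected drug: Imprime PGG against its Investigator's Brochure and Section 6.1, rituximab against its package insert and Section 6.2.
2. Define unexpected as the exact complement of expected. An event not listed for the suspected drug, or more severe or more specific than listed, is unexpected. If frequency or the consent form is kept as a criterion, it should enter this single definition, so that no event can meet both.
3. Replace the pointer to Section 6.1 with pointers to Sections 6.1 and 6.2, by drug.

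The consent form need not be removed, and no default is proposed for events that cannot be assigned to one drug; the sponsor should state how those are handled.

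The cost is an amendment to wording. Causality is already recorded by drug on the SAE form, so expectedness by drug adds one judgement per suspected drug. The downside is some additional expedited reports; their number cannot be estimated from the documents.
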